oncOPAL — Oncology Optimized Patient-Accessible Language

Study Protocol

Prospective Randomized Controlled Trial to Evaluate Locally Implemented Large Language Models (LLMs) for Simplifying Patient Communication in Hematology and Oncology

Date: 18.03.2026

Version: 1.0

Study Code: oncOPAL

Principal Investigators

Dr. med. [name]

PD Dr. med. [name]

TUM University Hospital (Klinikum rechts der Isar)

[name]

1 Protocol Synopsis

Short Title	oncOPAL
Title	Prospective Randomized Controlled Trial to Evaluate Locally Implemented Large Language Models (LLMs) for Simplifying Patient Communication in Hematology and Oncology
Study Center	TUM University Hospital (Klinikum rechts der Isar)
Study Design	Prospective, randomized controlled trial with parallel group design. Block randomization 2:1 (intervention : control) with permuted blocks of variable size (4–6). Additionally, a non-randomized translation arm for non-German-speaking patients.
Study Population	Inpatients of the Department of Medicine III (Hematology/Oncology) at TUM University Hospital who receive a discharge letter including the sections Current Status, Medical History, Epicrisis, and Further Management as part of routine clinical care.
Rationale	Up to 40–80% of medical information is not correctly recalled or understood by patients. LLMs can convert medical texts into plain-language versions with high accuracy. However, prospective RCTs evaluating the clinical benefit of LLM-simplified patient synopses are lacking.
Primary Objective	To evaluate the superiority of LLM-generated, simplified patient synopses over standard synopses with respect to patient comprehension.
Intervention	Intervention group: The following sections of the discharge letter are simplified by the LLM system: Current Status, Medical History, Epicrisis, and Further Management. The patient receives the LLM-

	simplified version in addition to the standard synopsis (after physician review). Control group: Standard synopsis only. Translation arm: LLM-simplified and translated synopsis of the same sections.
Sample Size	180 patients (150 randomized: 100 intervention, 50 control; 30 translation arm)
Primary Endpoint	Comprehension score (5-item scale, 10-point Likert, based on PEMAT)
Secondary Endpoints	Patient satisfaction (EORTC QLQ-INFO25 subscales), uncertainty reduction, format preference, physician review workload, correction rate, translation quality
Statistical Analyses	t-test / Mann-Whitney U-test for primary endpoint; chi-squared / Fisher for categorical endpoints; multivariate regression adjusted for educational level and further covariates; ITT analysis. Analysis with R or SPSS.
Study Duration	12 months recruitment (April 2026 – March 2027), data analysis complete June 2027

2 Rationale

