3.3 Endpoints

Primary Endpoint:

Comprehension score of the patient synopsis, measured using a 5-item scale (10-point Likert, based on PEMAT). The score is calculated as the mean of five items: overall comprehension, comprehension of the diagnosis, the treatment, the next steps, and medical terminology.

Secondary Endpoints:

- Patient satisfaction (EORTC QLQ-INFO25 subscales)
- Subjective uncertainty reduction (single item, 0–10 scale, measured before and after reading the synopsis)
- Preference for synopsis format (categorical variable)
- Health literacy as a covariate (HLS-EU-Q6)
- Time for physician review (in minutes) and correction rate
- Translation quality (rated by native-speaker reviewers, 5-point scale)

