3.4 Hypotheses

H1: LLM-simplified patient synopses achieve a significantly higher comprehension score (difference of at least 1.5 points on the 10-point scale) compared to standard synopses.

H0: There is no difference or a difference of less than 1.5 points between the groups.

4 Study Procedures

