4.2 Study Procedures

Potential participants are identified during inpatient stays in the Department of Medicine III. Following verification of inclusion and exclusion criteria, informed consent is obtained in writing (with a reflection period of at least 24 hours). Randomization or assignment to the translation arm then follows.

Day 0 (as part of the regular hospital visit):

- Informed consent procedure (approx. 10–15 minutes)
- Randomization or assignment to the translation arm
- Preparation of the synopsis as part of routine clinical care
- LLM simplification and physician review where applicable
- Distribution of synopsis/synopses with at least 15 minutes reading time
- Completion of the questionnaire (approx. 5–10 minutes)

No further study visits are planned. Study participation is complete upon submission of the questionnaire.

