7.3 Data Collection and Storage

Data collected include: demographic data (age, sex, educational level, native language), clinical baseline data (diagnosis, treatment setting), questionnaire data, and interview data where applicable. All study data are pseudonymized (study code oncOPAL-XXXX) and stored in a password-protected electronic database on servers of the Klinikum rechts der Isar. Data transmission is encrypted (TLS 1.3).

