7.7 Access Control

Access to study data is protected by individual user accounts with strong passwords and is logged. Servers are located in a secured data center with access control.

8 Benefit-Risk Assessment

The benefit-risk ratio is favorable. Participants in the intervention group and translation arm receive an additional plain-language synopsis that can promote understanding of diagnosis and treatment. Study participation involves minimal burden (additional time requirement of approximately 5–15 minutes). There are no physical risks. Psychological risks are low; the risk of possible misunderstandings arising from the simplified presentation is mitigated by mandatory physician review. Routine clinical care remains completely unchanged.

9 Sample Size and Power Analysis

The sample size calculation is based on the following assumptions: a clinically relevant difference in the primary endpoint of 1.5 points, an expected standard deviation of 2.5 points, power of 80%, significance level $\alpha = 0.05$ (two-sided), a randomization ratio of 2:1, and an expected dropout rate of 10%.

For a two-sided t-test for independent samples, the required sample size is $n = 136$ (91 intervention, 45 control). Accounting for the dropout rate, $n = 150$ patients will be recruited for the randomized part.

For the translation arm, $n = 30$ patients will be enrolled. This sample size permits a descriptive evaluation of feasibility without a formal statistical comparison.

10 Funding

The study is funded through internal resources of the Institute for Diagnostic and Interventional Radiology and the Department of Medicine III at TUM University Hospital (Klinikum rechts der Isar). There are no conflicts of interest.

11 References

1. Kessels RPC. Patients' memory for medical information. J R Soc Med. 2003;96(5):219-222.
2. Jeblick K, et al. ChatGPT Makes Medicine Easy to Swallow: An Exploratory Case Study on Simplified Radiology Reports. Radiology. 2024;308(1):e230618.

3. Ayers JW, et al. Comparing Physician and Artificial Intelligence Chatbot Responses to Patient Questions Posted to a Public Social Media Forum. *JAMA Intern Med.* 2023;183(6):589-596.
4. Arraras JL, et al. The EORTC QLQ-INFO25: A questionnaire to assess information given to cancer patients. *Eur J Cancer.* 2010;46(15):2726-2738.
5. Basch E, et al. Overall Survival Results of a Trial Assessing Patient-Reported Outcomes for Symptom Monitoring During Routine Cancer Treatment. *JAMA.* 2017;318(2):197-198.

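### The primary test is left as an unadjusted either/or; naming one linear model with baseline covariates the trial already plans to collect would fix a single answer in points and gain some precision.

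*Protocol*

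**What the plan says.** The Statistical Analyses row of the synopsis (section 1) gives "t-test / Mann-Whitney U-test for primary endpoint". No condition says which of the two applies. The same row lists "multivariate regression adjusted for educational level and further covariates"; it does not say for which endpoint, whether the model is primary, secondary or a sensitivity analysis, or what the further covariates are.

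Section 3.3 defines the comprehension score: "The score is calculated as the mean of five items". Section 3.4 states the hypothesis as a "difference of at least 1.5 points on the 10-point scale". Section 9 sizes the trial "For a two-sided t-test for independent samples", but does not say that this will be the final primary analysis.

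Two plausible predictors of the score are planned. Section 3.3 lists "Health literacy as a covariate (HLS-EU-Q6)", and section 7.3 lists "demographic data (age, sex, educational level, native language)". Section 4.2 shows one questionnaire step on Day 0, "Completion of the questionnaire (approx. 5–10 minutes)", placed after randomisation and after the synopsis has been read. No time is given for HLS-EU-Q6. Section 4.1 describes permuted-block 2:1 randomisation with no stratification factor named, and says that blinding of participants is not possible.

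**The concern.** Three analyses can each be presented as the trial's result: the t-test, the rank test and the adjusted regression. They do not all estimate the same thing. The t-test and the linear model estimate a difference in mean score, in points. The Mann-Whitney test concerns the probability that a score in one group exceeds a score in the other. It yields no mean difference that could be set against 1.5 points, so if that branch is taken, the primary result is no longer on the scale of the hypothesis and the sample size.

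Neither named test uses education or health literacy. If these predict comprehension, a model that includes them gives a narrower interval from the same patients. Precision that needs almost no extra data is then left unused in the primary result.

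**Working it through.** **Inputs.** From section 9: difference 1.5 points, SD 2.5, two-sided alpha 0.05, power 80%, allocation 2:1, dropout 10%. From the synopsis: 100 and 50 randomised. After 10% dropout: 100 × 0.9 = 90 and 50 × 0.9 = 45. R², the share of outcome variance explained by the covariates, is not in the protocol; 0.05 to 0.20 is an assumption.

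**1. The plan's own figure.** With k = 2 patients on intervention per control patient, the control-arm size is n = (z₀.₉₇₅ + z₀.₈₀)² × SD² × (1 + 1/k) / Δ² = (1.960 + 0.842)² × 6.25 × 1.5 / 2.25 = 32.7. This gives 33 + 66 = 99 patients, or 34 + 67 = 101 with the exact t distribution. The stated 136 (91 + 45) is not reproduced. At 91 and 45 the t-test has 90.5% power for 1.5 points, not 80%. That discrepancy is a separate matter, but it bears on the size of the gain here: at the stated SD the trial starts from about 90% power.

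**2. Precision with and without covariates (90 and 45).** SE = SD × √(1 − R²) × √(1/90 + 1/45). Unadjusted: 2.5 × √0.03333 = 2.5 × 0.18257 = 0.456. Equivalent sample size relative to unadjusted = 1/(1 − R²). Power is from the noncentral t distribution.

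| Assumed R² | SE | Equivalent extra patients | Power at 1.5 points | Power at 1.25 points |
|---|---|---|---|---|
| 0 | 0.456 | – | 90.4% | 77.6% |
| 0.05 | 0.445 | 5% | 91.7% | 79.7% |
| 0.10 | 0.433 | 11% | 93.0% | 81.8% |
| 0.20 | 0.408 | 25% | 95.4% | 86.0% |

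The 1.25-point column is illustrative; the protocol does not use that value. It shows that the gain matters more if the true effect is below the planned one.

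**3. What the either/or costs.** In 20,000 simulated null trials at 91 and 45, each test alone held about 5%. Reporting whichever p-value was smaller gave 6.0% with normal data and 6.2% with a skewed, ceiling-limited five-item score. The two tests disagreed on significance in 2.0% to 2.5% of null trials, and in about 6% of trials with a true difference of 1.0 point (5,000 runs, normal data). Choosing by a normality pre-test gave about 5.1% to 5.2% (8,000 null trials at 90 and 45).

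**4. Are the covariates safe to adjust for?** Group assignment cannot alter a patient's educational level. HLS-EU-Q6 is self-reported and has no stated time. The only questionnaire step in section 4.2 follows reading, and patients know what they received. If HLS-EU-Q6 is completed then, the intervention could affect the answers, and adjusting for them could bias the group difference. As written, only education is clearly safe.

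**The case against.** An unadjusted two-sample comparison in a randomised trial is valid. Its standard error already allows for chance imbalance, so such imbalance is ordinary sampling variation and not a defect of the test. On this view a covariate-adjusted primary model is a preference. This stands in part: the t-test would not be wrong, and the precision argument is one of efficiency, not validity.

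A selection rule, the covariate list and the role of the regression may be in a statistical analysis plan that is not shown, and the t-test in section 9 hints at a default. That too is fair. But the protocol does not simply leave the primary test open. It names two tests, one of which is not on the scale of its own hypothesis.

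Three stronger readings are tempting, and the protocol does not support them:

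- **Type I error is inflated.** This would follow only if the smaller p-value were reported, which the protocol does not say. A conventional pre-test rule costs almost nothing.
- **Adjustment is only secondary.** The protocol gives the regression no role at all.
- **The trial is underpowered without adjustment.** At 1.5 points and SD 2.5 the unadjusted t-test already has about 90% power.

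Finally, section 3.4 places differences below 1.5 points within the null hypothesis. The model proposed here tests against zero, so it does not settle that question. It does give an interval in points that can be compared with 1.5, as the t-test's interval also would.

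**Conclusion.** The point holds as one of choice and precision of the primary analysis. The protocol names two unadjusted tests without a rule, one of which does not estimate a difference in points, and lists an adjusted model without a role. Naming one model gives a single prespecified estimate on the scale of the hypothesis, and that benefit does not depend on R².

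The precision gain does depend on R²: small at 0.05 (SE 2.5% lower), modest at 0.10 (5% lower), and worthwhile at 0.20 (11% lower, equal to 25% more patients). These figures assume SD 2.5, 90 and 45 evaluable patients, and covariates unaffected by the intervention. For HLS-EU-Q6 that last condition is not secured by the current schedule. The change is worth making before data are seen; it does not correct an invalid test.

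**What to change.** Name one primary analysis: a linear regression of the comprehension score on randomised group and educational level, plus the HLS-EU-Q6 score provided it is completed before randomisation, or at least before the synopsis is handed out. Report the adjusted mean difference in points with its 95% CI, at two-sided alpha 0.05. Fix the coding of both covariates and replace the open reference to further covariates with a closed list. Keep the unadjusted t-test and the Mann-Whitney test as sensitivity analyses.

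State the time of HLS-EU-Q6 in section 4.2. If it has to stay after reading, leave it out of the primary model and adjust for education only.

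Cost: revised wording, slightly more analysis work, and moving one short instrument forward. Section 3.3 already requires the uncertainty item before reading, so some contact at that point is implied. Completing HLS-EU-Q6 before randomisation may need its own short step.

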2.1 Background

Communicating complex medical information to patients represents a central challenge in oncology. Studies show that up to 40–80% of the medical information conveyed during a physician consultation is not correctly recalled or understood by patients (Kessels 2003). This is particularly relevant in hematology and oncology, where complex treatment regimens, prognoses, and side-effect profiles must be communicated, making comprehensible written summaries especially important.

Large language models (LLMs) have made substantial progress in processing and generating natural language over recent years. Current studies demonstrate that LLMs can translate medical technical texts into plain language with high accuracy (Jeblick et al. 2024). A systematic review by Ayers et al. (2023) showed that LLM-generated responses to patient questions were in some cases rated higher in quality and empathy than responses from physicians.

Local implementation of LLMs (on-premise) enables the processing of sensitive patient data in compliance with the GDPR, as no data are transmitted to external servers.

2.2 Derivation of the Research Question

Despite promising results in retrospective analyses, prospective, randomized controlled trials evaluating the benefit of LLM-simplified patient synopses in routine clinical practice are lacking. The present study addresses this research gap. In addition, a non-randomized arm will evaluate the feasibility and quality of LLM translations for patients with insufficient German language proficiency.

3 Study Objectives

3.1 Primary Objective

To evaluate the superiority of LLM-generated, simplified patient synopses over standard synopses with respect to patient comprehension in hematology and oncology.

3.2 Secondary Objectives

- Assessment of patient satisfaction with the information received
- Evaluation of the subjective reduction in uncertainty and anxiety
- Assessment of patient preference for synopsis format
- Measurement of the time required for physician review of LLM-generated synopses
- Documentation of the rate of necessary physician corrections
- Qualitative assessment of LLM translations by native-speaker reviewers

3.3 Endpoints

Primary Endpoint:

Comprehension score of the patient synopsis, measured using a 5-item scale (10-point Likert, based on PEMAT). The score is calculated as the mean of five items: overall comprehension, comprehension of the diagnosis, the treatment, the next steps, and medical terminology.

Secondary Endpoints:

- Patient satisfaction (EORTC QLQ-INFO25 subscales)
- Subjective uncertainty reduction (single item, 0–10 scale, measured before and after reading the synopsis)
- Preference for synopsis format (categorical variable)
- Health literacy as a covariate (HLS-EU-Q6)
- Time for physician review (in minutes) and correction rate
- Translation quality (rated by native-speaker reviewers, 5-point scale)

3.4 Hypotheses

H1: LLM-simplified patient synopses achieve a significantly higher comprehension score (difference of at least 1.5 points on the 10-point scale) compared to standard synopses.

H0: There is no difference or a difference of less than 1.5 points between the groups.

4 Study Procedures

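### Section 3.4 makes 1.5 points a margin to be exceeded, while section 9 sizes an ordinary test against zero with 1.5 as the difference to detect, so the success criterion contradicts itself

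*Protocol*

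**What the plan says.** Protocol section 3.4 defines the alternative as a "significantly higher comprehension score (difference of at least 1.5 points on the 10-point scale) compared to standard synopses" and the null as "H0: There is no difference or a difference of less than 1.5 points between the groups".

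Section 9 bases the sample size on "a clinically relevant difference in the primary endpoint of 1.5 points", "an expected standard deviation of 2.5 points", 80% power, a two-sided alpha of 0.05, "a randomization ratio of 2:1" and 10% dropout. It applies a two-sided t-test for independent samples and arrives at 136 evaluable patients (91 and 45), with 150 randomized. It mentions neither a shifted null nor an assumed true effect above 1.5.

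The synopsis gives the primary analysis as "t-test / Mann-Whitney U-test for primary endpoint", again without a margin. The primary objective in section 3.1 is superiority, with no minimum size attached.

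**The concern.** One number is used in two incompatible ways. In section 3.4, 1.5 points is the edge of the null region. In section 9, it is the effect the trial is built to detect. Neither test in the synopsis, run in the usual way, tests the null of section 3.4: rejecting zero does not show that the difference is at least 1.5.

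Three success rules can be read from the text:

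- **A.** Reject a difference of zero (sections 3.1 and 9, synopsis).
- **B.** Reject every difference below 1.5 (section 3.4, H0 as written).
- **C.** Reject zero and also observe at least 1.5 points (a possible reading of H1).

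They can give opposite answers on the same data. If the rule is settled only once the result is known, the primary conclusion is open to choice.

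**Working it through.** **Inputs.** SD 2.5, planning difference 1.5, two-sided alpha 0.05 and 2:1 allocation, all from section 9. Evaluable patients: 100 and 50 less 10% dropout, which gives 90 and 45. Section 9's own split of 91 and 45 gives nearly the same results.

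**The plan's own figure.** Against a null of zero, with 2:1 allocation, the control-group size is

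n = (1.960 + 0.842)² × 2.5² × (1 + 1/2) / 1.5² = 32.7, rounded up to 33.

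That is 99 patients in total, or 102 by the exact t calculation. The stated 136 is not reproduced at 80% power. It is close to what 90% power against zero requires (132 by normal approximation, 135 by exact t). This discrepancy is a separate matter, but it explains why the power below is 90% and not 80%.

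**Which null section 9 used.** The section does not write its null out. If the null were 1.5 and the true difference also 1.5, the distance to be detected would be 1.5 − 1.5 = 0 and no finite sample size would give 80% power. A finite 136 is possible only with a null below 1.5, and zero is the default for the test named.

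**Standard error and critical value.**

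SE = 2.5 × √(1/90 + 1/45) = 0.456; t(0.975, 133 df) = 1.978; product = 0.90.

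**Rule A, null of zero.** Significant from an observed difference of 0.90. Noncentral-t power at a true 1.5: 90%.

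**Rule B, null as written.** The lower 95% limit must clear 1.5, so the observed difference must exceed 1.5 + 0.90 = 2.40. Power follows from the same t-test with noncentrality (true difference − 1.5)/SE:

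| True difference | Probability of rejecting the H0 of section 3.4 |
|---|---|
| 1.5 | 2.5% (5% if one-sided at 0.05) |
| 2.0 | 19% |
| 2.5 | 59% |
| 2.79 | 80% |

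The true differences above 1.5 are illustrative assumptions; the protocol gives none. With a true difference of 2.0, 80% power against the margin needs a control group of (1.960 + 0.842)² × 2.5² × 1.5 / 0.5² = 294.3, rounded up to 295, hence 3 × 295 = 885 evaluable patients. With 2.5 it needs 222, and with 3.0 it needs 99.

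**Rule C, significant and estimate at least 1.5.** Since 1.5 lies well above 0.90, the second condition governs. At a true 1.5 the estimate falls above 1.5 about half the time, so power is about 50%.

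**Where the rules collide.** Observed differences between 0.90 and 2.40 meet rule A and fail rule B. If the true difference is 1.5, the chance of landing there is about 90% − 2.5% = 88%. For example, an observed 1.2 points gives t = 1.2/0.456 = 2.63, p about 0.01, and a 95% confidence interval of 1.2 ± 0.90, or 0.30 to 2.10. That is superiority by section 3.1 and the synopsis, yet the H0 of section 3.4 stands.

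**The case against.** The objective, the sample size and the synopsis all point to ordinary superiority, and only section 3.4 is out of line. No passage asks for a lower confidence limit above 1.5, so in practice the ordinary t-test would be run and the 2.5% describes a test nobody plans. That figure is also true by construction: at the boundary of any null, the rejection probability equals the type I error rate, whatever the sample size. Section 9 calls 1.5 clinically relevant, not expected. H1 can be read more mildly as rule C. The figures for 2.0 points and above rest on effects the protocol never assumes.

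Much of this is fair. The 2.5% shows that the margin and the planning difference coincide; it does not measure a weakness of this design in particular. The likelier harm is a disputed conclusion, not a trial that cannot succeed. But the objection does not remove the contradiction. If the ordinary t-test is run, rejection does not establish H1 as written. Rule C has yet another power, about 50%, for which section 9 does not plan. A statistical analysis plan, which may exist but is not at hand, could not repair this alone, because whichever reading it chose would contradict a statement in the protocol.

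**Conclusion.** The hypotheses in section 3.4 and the test sized in section 9 contradict each other, and this must be resolved before any data are seen because it decides what the trial may conclude. At a true difference of 1.5, the probability of success is 90%, about 50% or 2.5%, depending on which statement is followed. The conflict covers observed differences from about 0.90 to 2.40 points, and the planning difference lies in the middle of that range.

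These figures assume the protocol's SD of 2.5, 90 and 45 evaluable patients, and a t-test on means. That section 9 used a null of zero is an inference, but a firm one. The contradiction itself can be read from the text and depends on none of these numbers.

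**What to change.** Rewrite section 3.4 to match the objective, the sample size and the synopsis:

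- H0: the mean comprehension scores are equal in the two groups. H1: they differ. Two-sided alpha 0.05; superiority is concluded if the 95% confidence interval for intervention minus control lies entirely above zero.
- State that 1.5 points is the planning difference of section 9. Report the estimate and its 95% confidence interval against 1.5 to interpret clinical relevance, not as part of H0.

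This decision rule is about means and goes with the t-test. If the Mann-Whitney test stays as a possible primary test, the hypothesis and the rule have to be worded to fit it, because it does not test equality of means.

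The cost is two sentences in the protocol, with no change to sample size, procedures or data collection.

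If the sponsor does intend to show a difference above 1.5, section 3.4 can stay. Section 9 and the analysis would then need a test shifted to 1.5 and a justified true effect above 1.5. The sample size would have to be recalculated and could be several times larger.
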